9.6 Record retention

Upon closure of the study, the investigator must maintain all study site records in a safe and secure location. The investigator is responsible for the integrity, retention, and security of all study-related records. The investigator must ensure that any reproductions of the original records are legible and provide a true and accurate copy of the original. Accurate, complete, and current records must be stored in such a way as to permit easy and timely retrieval for the sponsor or any applicable regulatory authorities.

The sponsor will inform the investigator of the time period for retaining these records to comply with all applicable regulatory requirements, with the minimum retention time being the longest of those times dictated by institutional requirements, local laws or regulations, or the sponsor's standard procedures. The investigator must notify the sponsor in the event of any changes to archival arrangements due to withdrawal of the investigator's responsibility for keeping study records to ensure that suitable arrangements for the retention of study records are made.

9.7 Publication policy

The study protocol, study data, and information related the study or the sponsor's products or research programs are to be kept confidential and may not be disclosed without the consent of the sponsor. The investigators have the responsibility to provide complete study data, records, and reports for inspection by the appropriate regulatory authorities, the sponsor, or the IEC/IRB, as appropriate.

The investigator agrees that the results of this study may be used for submission to national or international registration and supervising authorities. The sponsor may disclose the information obtained during the study to regulatory authorities or other personnel as required. If necessary, the sponsor may disclose the names, contact information, and qualifications of all investigators as well as their roles in the study. Upon completion of the study, publication or disclosure of the study results is to follow the terms contained in the sponsor's publication policy.

9.8 Financial disclosure

The US FDA Financial Disclosure by Clinical Investigators (21 CFR 54) regulations require sponsors to obtain certain financial information from investigators participating in covered clinical studies. By participating in the study, the investigator agrees to provide the required financial information and to promptly update the sponsor with any relevant changes to this financial information throughout the course of the study and for up to 1 year after its completion if necessary.

9.9 Investigator compliance

The investigator will conduct the study in compliance with the protocol provided by the sponsor and in accordance with all relevant regulatory guidelines and requirements.

Modifications to the protocol should not be made without the agreement of the investigator and sponsor. The sponsor will submit all protocol modifications to the appropriate regulatory authority in accordance with applicable regulations. All protocol modifications require written IEC/IRB approval/favorable opinion, except in the case of an immediate hazard to subjects.

If an immediate deviation from the protocol is required to eliminate an immediate hazard to subjects, the investigator must contact the sponsor, if possible, to discuss the planned course of action. The investigator must thoroughly document any departure from the protocol and submit appropriate documentation to the sponsor without delay.

10 APPENDICES

1 LIST OF ABBREVIATIONS

Abbreviation/Term	Definition
AE	Adverse event
ATC	Anatomical Therapeutic Chemical classification system of the World Health Organization
BMI	Body mass index
CSR	Clinical study report
CTR	Common treatment response
eCRF	electronic case report form
FACE-Q	Set of subject-reported questionnaire modules
GAIS	Global Aesthetic Improvement Scale
IOH	Infraorbital hollow

ITT	Intent-to-Treat
MedDRA	Medical Dictionary for Regulatory Activities
MIHAS	Merz Infraorbital Hollow Assessment Scale
n imp	Number of imputed values
n miss	Number of missing values
n obs	Number of observed values
OC	Observed case
PDF	Portable document format
PP	Per protocol Population
PT	Preferred term
SAE	Serious adverse events
SAP	Statistical analysis plan
SAS®	Statistical Analysis System software
SD	Standard deviation
SP	Safety Population
SOC	System organ class
TFLs	Tables / figures / listings
TEAE	Treatment emergent adverse event

2 GENERAL AND TECHNICAL ASPECTS

The objective of this statistical analysis plan (SAP) is to specify the statistical analyses with appropriate detail and precision to serve as a guideline for statistical programming and creation of tables, figures, and listings for clinical study protocol M930121001, dated 13-Mar-2017 and the following amendments, dated 09-Aug-2017, 05-Dec-2017, 04-Oct-2018, and 08-Nov-2018.

The Merz standard Table, Figures, and Listings (TFLs) for medical devices, version 1.0 (29.06.2018) will be applied and adapted to study specific requirements as laid down in the clinical study protocol and any amendments.

3 CLINICAL STUDY DESIGN AND OBJECTIVES

3.1 Clinical Study Design

This is a prospective, [REDACTED] multi-center, randomized-controlled study in subjects with moderate to severe infraorbital hollow (IOH) deficit. Approximately 66 subjects will be enrolled from 3 sites in the United States. Subjects will be randomized to either a treatment group or an untreated control group using a 2:1 (treatment: control) allocation ratio. Approximately 70% of the total sample size will consist of subjects with a Fitzpatrick skin type of I, II, or III and approximately 30% of the subjects will be Fitzpatrick skin type IV, V, or VI. Subjects from the Fitzpatrick skin type IV, V, and VI group will be distributed as follows: ≥ 6 subjects will be enrolled in the IV Fitzpatrick skin type group and ≥ 12 subjects will be enrolled with Fitzpatrick Skin Types V and VI Fitzpatrick skin type group. Each clinical site will enroll a minimum of 6 subjects with Fitzpatrick skin types IV, V, VI. At least 5 males will be enrolled into the study.

For subjects randomized to the treatment group, both right and left IOHs will receive treatment with Belotero Balance. To achieve symmetrical correction a touch-up injection will be given, with the subject's consent, in one or both IOHs if the treating investigator determines a treated subject has asymmetrical IOHs based on a visual assessment.

[figure not shown]
For the primary effectiveness assessment, IOH deficit will be assessed according to the Merz Infraorbital Hollow Assessment Scale (MIHAS) [REDACTED]

The treated subjects will have a safety phone call 72 hours after baseline treatment and in-clinic safety visits at Week 2 and Months 2, 3, 6, 9, and 12 post baseline injection. Effectiveness assessments will be performed in clinic at baseline and Month 2 post baseline injection. [REDACTED]

All treated subjects will be assessed 1 month after baseline injection for asymmetry and safety. If a treated subject receives a touch-up injection for asymmetric correction the visits schedule will be re-calculated relative to the touch-up visit (i.e., 72 hour phone call, 2 weeks, Months 1, 2, 3, 6, 9 and 12). For these subjects effectiveness assessments will occur at baseline and 2 months after the touch-up injection.

If subjects report a safety concern during the 72-hour phone call, an unscheduled visit will be scheduled to bring the subject into the clinic to address safety concerns.

Control-group subjects will be evaluated at enrollment and Month 2 in the clinic. [REDACTED]

3.2 Clinical Study Objectives

[figure not shown]
The pilot study aims to define safety, effectiveness, and patient-reported outcomes for Belotero Balance use in the IOH [REDACTED]
[REDACTED].

3.2.1 Effectiveness

The effectiveness and relevance of aesthetically pleasing outcomes following Belotero Balance injection will be established in the following manner:

- The primary endpoint will establish effectiveness by using the MIHAS to demonstrate that clinically relevant changes of ≥ 1 -point on both IOHs can be detected 2-months post-treatment [REDACTED]
[REDACTED].
- The secondary endpoints including the validated FACE-Q satisfaction with eyes, the investigator GAIS, and the subject GAIS will be utilized to substantiate aesthetically pleasing outcomes. [REDACTED]
[REDACTED]
[REDACTED]
[REDACTED]
[REDACTED]

Additionally, the investigator and subject GAIS scores at Month 2 post last injection visit will be utilized to demonstrate the level of improvement, when compared to baseline photographs, resulting from treatment in the IOHs.

In totality, the results from the MIHAS [REDACTED] obtained from the treating investigator and subject perspectives regarding aesthetic improvements, will be used to establish that Belotero Balance injections in the IOH region are effective in producing clinically relevant and aesthetically pleasing outcomes.

3.2.2 Safety

The safety objectives include the identification and description of adverse events (AEs) and serious adverse events (SAEs) during the course of the study. In addition to standard safety assessments, eye assessments (including visual acuity, visual field, ocular motility, and undilated fundoscopic exam) will be evaluated. Common treatment responses (CTRs) will also be assessed.

4 DETERMINATION OF SAMPLE SIZE

In order to assess the ability of the planned sample size to provide power for a statistical comparison of the treatment and control groups success proportions (based on a ≥ 1 -point improvement on both IOHs using the MIHAS from baseline to Month 2), a power calculation using a Fisher's exact test with a binomial distribution was performed using the following assumptions:

- Type I error rate: 0.05 (two-sided)
- Control group success proportion: 0.20
- Treatment group success proportion: 0.60
- Allocation ratio (control: treatment): 1:2
- Total N (number of evaluable subjects): 60 (40 subjects in the treatment group and 20 subjects in the control group).

Based on the above assumptions, the study power is approximately 80%. To account for possible missing data, attrition, and/or study deviations (up to 10%), a total of 66 subjects will be enrolled (44 subjects in the treatment group and 22 subjects in the no treatment control arm).

Approximately 70% of the total sample size will consist of subjects with a Fitzpatrick skin type of I, II, or III, and approximately 30% of the subjects will consist of subjects with a Fitzpatrick skin type IV, V, or VI. Subjects from the Fitzpatrick skin type IV, V, and VI group will be distributed as follows: ≥ 6 subjects will be enrolled in the Fitzpatrick skin type group IV and ≥ 12 subjects will be enrolled in the Fitzpatrick Skin Type group V and VI. Each clinical site will enroll a minimum of 6 subjects with Fitzpatrick skin types IV, V, VI. At least 5 males will be enrolled into the study.

In the event that the sample size accounting for missing data, attrition, and/or deviations is attained (i.e., 44 treated subjects and 22 untreated/control subjects), using the assumptions above, the study power would be approximately 84%.

nQuery 8, Statistical Solutions Ltd., was used for the power calculation.

4.1 Randomization

The randomization procedure for this study was a block randomization stratified per site which was computer-generated independently of the study team. Block randomization controlled for potential deviations from the intended allocation ratio between treated and control subjects. Accordingly, a 2:1 allocation ratio was utilized with approximately 44 subjects randomized to treatment and 22 subjects to control.

5 ANALYSIS SETS

The following analysis sets are defined for the statistical analysis of this clinical study:

Safety Population (SP)

The SP consists of all randomized subjects who received at least one study treatment in the active treatment group or who were randomized into the control arm.

Intent-to-Treat Population (ITT)

The ITT consists of all randomized subjects. This will be the primary population used for the effectiveness analyses. All effectiveness endpoints will be analyzed as randomized.

Per Protocol Population (PP)

The PP is a subset of subjects in the ITT population without major protocol deviations. Final determination of what constitutes major or minor protocol deviations will be made prior to database lock.

Subjects which have not been treated according to the randomization list will be excluded from PP. In general, tables performed on the SP will present subjects as treated and tables performed on the ITT will present subjects as randomized. In the subject data listings, the randomized treatment arm will be listed except for the section 16.2.7 (Adverse events) and 16.2.8 (Other safety variables): here the actual treatment arm will be listed.

6 ENDPOINTS FOR ANALYSIS

Unless otherwise specified, for all effectiveness endpoints, Month 2 for treated subjects is from the time of last injection (i.e., either baseline treatment or touch-up, if applicable). For randomized and not treated subjects, the effectiveness assessments will be performed at Month 2 from the baseline visit.

6.1 Effectiveness Endpoints

6.1.1 Primary Endpoint

[figure not shown]
The primary endpoint is a comparison of the responder rate between the treatment group and the untreated control group at Month 2, according to the MIHAS [REDACTED]
[REDACTED].

Treatment response is defined as \geq 1-point improvement on the MIHAS scale for both IOHs compared to baseline

6.1.2 Secondary Endpoints

- Summary of the FACE-Q satisfaction with eyes scores for treated and control subjects at baseline and Month 2. The subject's assessment is based on taking into consideration both eyes.
- Descriptive summary of GAIS scores for treated subjects at Month 2, as completed by the treating investigator. [REDACTED]
[REDACTED]
- Descriptive summary of GAIS scores for treated subjects at Month 2, as completed by the subject. [REDACTED]
[REDACTED]
- Summary of the responder rates in the treatment group and the control group at Month 2, according to the MIHAS [REDACTED]
[REDACTED].

Treatment response is defined as \geq 1-point improvement on both IOHs when comparing the change from baseline to Month 2. A subject will be considered a responder if a treatment response of at least 1-point change on both IOHs is determined [REDACTED]
[REDACTED].

6.2 Safety Endpoints

- Incidence and nature of device- and/or injection-related AEs and SAEs observed during the study.
- Incidence, severity, and duration of pre-specified CTRs reported in subject diaries.

7 STATISTICAL ANALYSIS METHODS

The sponsor will finalize the formal SAP prior to database lock. Deviations from the analyses outlined in the study protocol are documented in this SAP.

Adequate descriptive statistics will be provided for each endpoint. Continuous variables will be summarized by number of observations, number of missing or number of imputed observations, mean, standard deviation, minimum, median, and maximum. Categorical data will be summarized in frequency tables using counts (n) and percentages (%). Ordered categorical data will be summarized by both.

If not otherwise specified Month 2 data refers to

- Month 2 post last injection visit (i.e., either baseline treatment or touch-up, if applicable) for subjects in the treatment group and
- Month 2 post baseline visit for subjects in the control group.

7.1 Effectiveness Endpoints

The primary efficacy analysis and all secondary endpoints will be based primarily on the ITT and additionally, for sensitivity purposes, on the PP. [REDACTED]

Statistical tests will be two-sided hypothesis tests for between-treatment arm differences in general. Continuous variables (values and changes from baseline) will be summarized by number of observed values (n obs), number of missing values (n miss)/ number of imputed values (n imp), mean, standard deviation (SD), median, minimum, and maximum. For qualitative variables, absolute and percent frequencies (n, %) including the number of missing values and, if applicable, shift tables also including the number of missing values will be displayed. Confidence limits and descriptive p-values will be given, where appropriate.

P-values will be reported to four decimal places (e.g., p=0.0375). P-values below 0.0001 will be presented as '<0.0001'.

Mean, median will be reported to one decimal place more than the data were collected, for the standard deviation two decimal places more will be displayed; for derived data, an adequate number of decimal places will be chosen. Percentages will be calculated using the denominator of all subjects in a specified population, or treatment arm. The denominator will be specified in a footnote to the tables for clarification if necessary. Percentages will be reported to one decimal place.

7.1.1 Primary Effectiveness Endpoint

The primary effectiveness endpoint, the response rate (proportion of subjects with ≥ 1 -grade improvement of both IOHs on the MIHAS from baseline to Month 2) will be summarized as percentages for the treatment ($p_{\text{treatment}}$) (coded with “TreatmentArm”=0) and control (p_{control}) (coded with “TreatmentArm”=1) subjects and inferentially compared according to the following hypothesis:

$$H_0 \text{ (null): } p_{\text{treatment}} \leq p_{\text{control}}$$

$$H_a \text{ (alternate): } p_{\text{treatment}} > p_{\text{control}}$$

For this hypothesis testing, the Fisher’s exact test will be used to compare both response rates in order to test for the superiority of treatment over control. If the left-sided p-value obtained from this test is < 0.025 , H_0 will be rejected in favor of H_a . The following SAS code will be used:

```
proc freq data = dataset;
  tables TreatmentArm*Response /fisher riskdiff(column=2 cl=newcombe) alpha=
                                0.05;
  ods output fishersexact = out pdiffcls=out1;run;
```

Assuming the response is coded with ‘1’ and no response is coded with ‘0’.

Furthermore, a two-sided 95% Newcombe based on Wilson scores confidence interval for the risk difference will be calculated. The primary analysis of the response rates at Month 2 will be based on the ITT, using the observed case (OC) values. The supportive analyses of primary effectiveness endpoint will be for the ITT using imputed (missing imputed as no change) and for the PP using the OC.

Moreover, the response rates for ITT (OC) at Months 2 will be provided for the following subgroups:

- Fitzpatrick Skin Types (I, II, III versus IV, V, VI)
- Gender

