8.4.1 Effectiveness analysis

8.4.1.1 Primary effectiveness endpoint

The primary effectiveness endpoint, the proportion of subjects with \geq 1-grade improvement of both IOHs on the MIHAS from baseline to Month 2 will be summarized as percentages for the treatment ($p_{\text{treatment}}$) and control (p_{control}) subjects and inferentially compared according to the following hypothesis:

$$H_0 \text{ (null): } p_{\text{treatment}} \leq p_{\text{control}}$$

$$H_a \text{ (alternate): } p_{\text{treatment}} > p_{\text{control}}$$

[figure not shown]
For this hypothesis testing, the Fisher's exact test will be used to compare both proportions in order to test for the superiority of treatment over control. If the two-sided p-value obtained from this test statistic is < 0.05 H_0 will be rejected in favor of H_a .

[figure not shown]

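### Optional gain: naming Boschloo's exact test instead of Fisher's in SAP 7.1.1 keeps the one-sided 0.025 limit and adds about 4 to 8 points of power over the SAP rule

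*SAP*

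**What the plan says.** Both documents name Fisher's exact test for the primary responder comparison: SAP 7.1.1 ("exact test will be used to compare both response rates") and protocol 8.4.1.1 ("exact test will be used to compare both proportions").

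The decision rules differ in form:
- SAP 7.1.1: "If the left-sided p-value obtained from this test is < 0.025", the null hypothesis is rejected. With the SAP's coding (treatment 0, non-response 0), the left tail is the superiority direction.
- Protocol 8.4.1.1: "If the two-sided p-value obtained from this test statistic is < 0.05", it is rejected.

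SAP 7.1.1 also states that "a two-sided 95% Newcombe based on Wilson scores confidence interval for the risk difference will be calculated". The interval accompanies the test and is not part of the decision rule.

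Protocol 8.1 and SAP section 4 base power on Fisher's test at two-sided 0.05, with response rates of 0.20 (control) and 0.60 (treatment). They state about 80% power for 40 treated and 20 control subjects, and about 84% if all 44 and 22 are evaluable. Neither document gives the attained type I error of the test or discusses an unconditional exact test.

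**The concern.** Fisher's test conditions on the total number of responders. With 60 to 66 subjects, the p-values available for a given total are few and widely spaced, so a cut-off of 0.025 is rarely met closely and the true error falls well below it. An exact unconditional test can use more of the same allowance without breaching it, which means more power at no cost in subjects.

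There is a reporting side as well. The Newcombe interval is not conservative in the same way, so the report could show a 95% interval excluding zero beside a primary test that fails. At 40/20, 24/40 versus 6/20 responders gives a one-sided Fisher p of 0.0269 (not rejected), while the Newcombe lower limit is 0.032 (above zero).

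**Working it through.** **Inputs** (protocol 8.1, SAP 4 and 7.1.1): response rates 0.60 and 0.20; sizes 40/20 (planned evaluable) and 44/22 (planned enrolment); SAP rule one-sided p < 0.025; protocol rule two-sided p < 0.05. The SAP's primary analysis uses observed cases, so the analysed size may fall between these pairs or near them.

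**Method.** Let x be responders among n_t treated, y among n_c controls, and s = x + y. All (n_t + 1)(n_c + 1) tables are enumerated.
- One-sided Fisher p(x, y) = sum over k ≥ x of C(n_t, k) C(n_c, s − k) / C(n_t + n_c, s).
- For a rejection region R, the error at a common rate π is the sum over R of Bin(x; n_t, π) Bin(y; n_c, π). The maximum type I error is the largest value over π from 0.0001 to 0.9999.
- Power is the sum over R of Bin(x; n_t, 0.60) Bin(y; n_c, 0.20).
- Boschloo's region is {p(x, y) ≤ c}, with c the largest value that keeps the maximum error at or below 0.025. This gives c = 0.0405 at 40/20 and 0.0408 at 44/22. Because c exceeds 0.025, the region contains every table that the SAP rule rejects (20 more tables at 40/20).

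**Step 1: the plan's own figures.** The SAP's Fisher rule gives 79.1% at 40/20 (stated about 80%) and 84.8% at 44/22 (stated about 84%). Both reproduce.

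**Step 2: attained error and power.**

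| Rule | 40/20 max error | 40/20 power | 44/22 max error | 44/22 power |
|---|---|---|---|---|
| Fisher, SAP, one-sided < 0.025 | 1.31% | 79.1% | 1.45% | 84.8% |
| Fisher, protocol, two-sided < 0.05 (superiority direction) | 2.26% | 81.3% | 2.13% | 87.4% |
| Boschloo, one-sided 0.025 | 2.49% | 86.9% | 2.44% | 89.1% |
| Unconditional pooled-Z | 2.26% | 84.0% | 2.33% | 88.8% |
| Unconditional unpooled-Z | 1.71% | 73.9% | 1.75% | 79.5% |

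The SAP rule uses 0.0131/0.025 = 52% of its allowance at 40/20 and 0.0145/0.025 = 58% at 44/22.

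Boschloo's gain, from unrounded powers:
- over the SAP rule: 86.89 − 79.10 = 7.8 points, and 89.05 − 84.83 = 4.2 points;
- over the protocol rule: 86.89 − 81.26 = 5.6 points, and 89.05 − 87.42 = 1.6 points.

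The two Fisher rules are not equivalent under 2:1 allocation. They differ on 12 tables at 40/20 and 15 at 44/22.

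**Step 3: dependence on size** (gain over the SAP rule).

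| Size | Fisher | Boschloo | Gain (points) |
|---|---|---|---|
| 38/19 | 79.2% | 84.8% | 5.6 |
| 39/20 | 79.9% | 85.2% | 5.3 |
| 40/19 | 78.5% | 85.0% | 6.5 |
| 41/20 | 81.1% | 86.5% | 5.4 |
| 42/21 | 82.3% | 87.6% | 5.3 |
| 43/22 | 83.9% | 89.4% | 5.5 |

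So 40/20 is a favourable size. If the effect is smaller, 0.50 versus 0.20, power goes from 53.1% to 63.2% at 40/20 and from 57.8% to 66.6% at 44/22.

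**Step 4: agreement with the Newcombe interval.** Under the planning rates, the probability that the SAP rule and the interval disagree is 8.5% at 40/20 and 4.8% at 44/22. In every such table the interval excludes zero and Fisher does not reject. With Boschloo it is 0.7% and 0.6%. The interval is itself approximate: rejecting when its lower limit exceeds zero has a maximum one-sided error of 2.74% and 2.93%.

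**The case against.** The best defence is that nothing here is wrong. Fisher's test controls the error, the sample size was calculated with it, the stated power reproduces, and this is a pilot meant to inform a pivotal design. All of that stands.

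The size of the gain also needs care. The 7.8 points belong to 40/20, the plan's full-attrition case. At planned enrolment the gain is 4.2 points, and against the protocol's own rule only 1.6.

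Three stronger readings are tempting, and the documents do not support them:
- A reader might infer that the plan as a whole leaves half its error unused. That describes the SAP rule only. The protocol's two-sided rule reaches 2.26% and 2.13% in the superiority direction, so part of the shortfall comes from the SAP's change of rule.
- A reader might infer that Boschloo would allow a smaller trial, because it has 81.5% power at 36/18 (54 subjects) against 79.1% for the SAP's Fisher rule with 60. The protocol's two-sided Fisher rule already has 80.9% at 36/18, so no saving in subjects should be claimed.
- A reader might put the interval conflict down to Fisher alone. Part of it arises because the Newcombe interval is slightly liberal. Since SAP 7.1.1 decides on the p-value alone, a mismatch is awkward to report but leaves the result unambiguous.

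Timing is a fair objection too. SAP 4.1 describes randomisation in the past tense, and moving to a test that rejects at Fisher p-values up to about 0.041 could look data-driven if made late. This limits when the change can be made. It does not count against the test itself.

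**Conclusion.** The point holds as an inexpensive efficiency improvement. At the same one-sided 0.025 limit, Boschloo's test loses no rejection that the SAP rule would make. It adds 7.8 points of power at 40/20, 4.2 at 44/22, and mostly about 4 to 7 at nearby sizes. Over the protocol's two-sided rule it adds 5.6 and 1.6 points. It also nearly removes disagreement with the Newcombe interval.

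These figures assume independent binomial responses, the planning rates of 0.60 and 0.20, and analysed numbers close to those planned. They are specific to Boschloo's ordering: pooled-Z gains less at 40/20, and unpooled-Z falls below Fisher. The results do not show that the plan is invalid or that its stated power is wrong.

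**What to change.** In SAP 7.1.1, name Boschloo's exact unconditional test as the single primary test, with the one-sided Fisher p-value as ordering statistic and a one-sided level of 0.025. Do this before any review of outcomes by arm and before database lock. The lock that matters is the temporary Month 2 lock in SAP 7.4.2, because the effectiveness analyses are run then.

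- Do not write a generic Barnard or unconditional-exact option. The choice of statistic moves power at 40/20 between 73.9% and 86.9%.
- Keep Fisher's test as a sensitivity analysis and the Newcombe interval as planned.
- Align protocol 8.4.1.1 with SAP 7.1.1 so that both state the same test and one decision rule. This is needed even if Fisher is kept, because the two present rules reject different tables.
- Record the reason and the date of the change. SAP section 7 already provides for documenting deviations from the protocol.

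Cost: no subjects and no visits. It takes revised wording and validated code, since the SAP's listed procedure call requests only Fisher's test. Readers get a less familiar p-value, and the primary test no longer matches the one behind the sample size, which the SAP should say openly.
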